8.5 Correlative Biomarker Analysis

An exploratory endpoint of the study is to evaluate the predictive accuracy of potential biomarkers for the PSA response and rPFS endpoints. Other exploratory objectives include assessment of mechanisms of resistance to Sacituzumab Govitecan via biomarker analysis of post-

progression tumor tissue. These analyses will be mostly descriptive for future references. All exploratory endpoints will be summarized using standard descriptive statistics, stratified by assessment time point. Longitudinal changes will be evaluated using a linear or generalized linear mixed effects model.

A Cox proportional hazards regression model (for the rPFS endpoint) and a logistic regression model (for the PSA response endpoint) will be used to assess the prognostic significance of baseline factors both alone and in combination with other biomarkers (e.g., clinical parameters, LDH, Hb). For each regression model, the c-index will be used to quantify the predictive accuracy of these biomarkers.

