2.3 Exploratory Objective

To associate predictive biomarkers with clinical outcomes to Sacituzumab Govitecan in CRPC subjects who have progressed while on enzalutamide, apalutamide, or abiraterone.

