8.3 Determination of Sample Size

The primary endpoints for the study are (1) PSA response rate, which is defined as the proportion of subjects achieving a $\geq 50\%$ decline in PSA at or within 9 weeks of starting Sacituzumab Govitecan. Prior published data from retrospective studies report PSA response rates ($\geq 50\%$ decline) in 20-30% of subjects on 2nd line AR directed therapy after progression on a 1st line agent in the pre-docetaxel setting (3-8), (2) and the 6-month rPFS rate. The response rate appears higher with cytotoxic chemotherapy. Although data are limited in the pre-docetaxel setting, retrospective studies in the post-docetaxel setting suggest patients with prior response to abiraterone are more likely to respond to second line enzalutamide (9-11). The familywise type I error for the two primary endpoints of the study is one-sided 0.05 and a Bonferroni adjustment for evaluating two primary endpoints will be applied that each endpoint will be tested at the one-sided 0.025 (0.05/2) significance level. A PSA response rate of 20% or less will be considered as unacceptably low. A PSA response rate of 40% or more, on the other hand, will be considered sufficient evidence to consider further clinical trial investigation. Hence, the null hypothesis that the PSA response rate is 20% will be tested against the alternative hypothesis that the PSA response rate is 40%. A sample size of 45 evaluable subjects for PSA response (defined as subjects who received at least 1 dose of Sacituzumab Govitecan and have at least 1 post-dose assessment of PSA) is required to detect an increase in the PSA response rate from 20% to 40% with 87% power at the one-sided exact test with a significance level of 0.025. Analogously, a 6-month rPFS rate of 20% or less will be considered as unacceptably low and 40% or more considered sufficient evidence. Again a sample size of 45 evaluable subjects (for assessing 6-month PFS rate) is required to detect an increase in the 6-month rPFS rate from 20% to 40% with 87% power at the one-sided 0.025 significance level. The following table shows the probabilities for rejecting the null hypothesis with a sample size of 45 evaluable subjects, assuming that the true PSA response/6-month rPFS rates range between 35-50%.

Table 10. Attainable power levels with a sample size of 45 evaluable subjects

True PSA response/6-months PFS rate	Probability of rejecting null hypothesis
35%	68%
40%	87%
45%	96%
50%	>99%

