8.4.3 Efficacy Analysis

The Efficacy Analysis Set will consist of all subjects who receive at least 1 dose of Sacituzumab Govitecan and have at least 1 post-dose assessment of PSA; and/or 1 post-dose radiographic assessment for subjects with evaluable and/or measurable metastases at screening, 1 post-dose assessment of metastatic disease will be required. Subjects who

discontinue study participation early so they do not meet criteria for inclusion in the efficacy analysis set can be replaced.

Changes in PSA will be compared to baseline and maximal change from baseline and change at Week 9 (e.g., end of Cycle 3) will also be determined, as will duration of response. Maximum change in soft tissue lesions as seen on CT or MRI of the chest, abdomen and pelvis, as well as changes on bone scintigraphy according to the PCWG2 criteria will also be compared to baseline, and summarized.

A subgroup efficacy analysis will be conducted in the group of patients who continued single agent ARSI in combination with Sacituzumab Govitecan.

Definition and analysis of primary efficacy endpoint:

PSA response rate: Subjects who achieve $\geq 50\%$ PSA decline at or before 9 weeks of therapy with Sacituzumab Govitecan are considered to have responded. PSA responses will be analyzed by descriptive statistics and summarized in tabular format (frequency tables). The overall PSA response rate will be reported along with the corresponding 95% confidence interval which will be constructed using the Wilson score method.

6-month rPFS rate: Proportion of subjects remaining alive and progression free (using PCWG2 criteria) 6 months from time of starting treatment as estimated by the Kaplan-Meier method. The point estimate of the 6-month rPFS rate will be reported along with the corresponding two-sided 95% confidence interval.

Definition and analysis of secondary efficacy endpoints:

- i. *Median rPFS.* The probability distribution of PFS will be estimated using the Kaplan-Meier method. The median will be estimated from this distribution. Subjects who have not died or progressed (using PCWG2 criteria) will be censored at the date of last assessment.
- ii. *Median OS.* OS is the duration from start of treatment until death from any cause. The probability distribution of OS will be estimated using the Kaplan-Meier method. The median will be estimated from this distribution. Subjects who have not died will be censored at the date of last contact.

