APPENDIX E: PROSTATE CANCER WORKING GROUP 2 (PCWG2) RESPONSE CRITERIA

The effects of Sacituzumab Govitecan will be assessed using both “control/ relieve/ eliminate” endpoints as well as “prevent/ delay” endpoints as outlined in the PCWG2 response criteria summarized in the table below.

Variable	PCWG2 (2007)
PSA	
Recognize that a favorable effect on PSA may be delayed for 9 weeks or more, even for a cytotoxic drug
 
Monitor PSA by cycle but plan to continue through early rises for a minimum of 9 weeks unless other evidence of progression
 
Ignore early rises (prior to 9 weeks) in determining PSA response
 
For control/relieve/eliminate endpoints:
 
Record the percent change from baseline (rise or fall) at 9 weeks, and separately, the maximal change (rise or fall) at any time using a waterfall plot
 
For prevent/ delay (progression): Decline from baseline: Record time from start of therapy to first PSA increase that is > 25% and > 2 ng/ml above the nadir, and which is confirmed by a second value 3 or more weeks later (i.e., a confirmed rising trend).
 
No decline from baseline: PSA progression > 25% and > 2 ng/ml after 9 weeks

Soft-tissue lesions	
For control/relieve/ eliminate endpoints: Use RECIST with caveats:
 
Only report changes in lymph nodes that were > 2 cm in diameter at baseline
 
Record changes in nodal and visceral soft tissue sites separately
 
Record complete elimination of disease at any site separately
 
Confirm favorable change with second scan
 
Record changes using waterfall plot
 
For prevent/ delay endpoints (progression): Use RECIST criteria for progression, with additional requirement that progression at first assessment be confirmed by a second scan 6 or more weeks later.
 
Note that for some treatments, a lesion may increase in size before it decreases

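### Section 8.5 relates baseline biomarkers to PSA outcome only through the 50% yes/no cut; a pre-specified analysis of the size of the PSA change beside it would cheaply recover some power

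*Combined protocol and SAP*

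**What the plan says.** Section 2.3 gives the single exploratory objective: "To associate predictive biomarkers with clinical outcomes to Sacituzumab Govitecan in CRPC subjects". Section 8.5 carries it out with two regressions, a Cox model for rPFS and, for PSA, the following: "a logistic regression model (for the PSA response endpoint) will be used to assess the prognostic significance of baseline factors". Both are to be fitted for single factors and in combination, and both are summarised by the c-index. Section 8.4.3 defines PSA response as a decline of at least 50% by 9 weeks, so the logistic outcome is binary. The mixed model in 8.5 covers changes over time in the exploratory endpoints; it does not link a baseline marker to the size of the PSA change.

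That size is nonetheless available. Section 8.4.3 states that "maximal change from baseline and change at Week 9 (e.g., end of Cycle 3) will also be determined", Section 6.3.1 names the same two measures, and Appendix E says: "Record the percent change from baseline (rise or fall) at 9 weeks, and separately, the maximal change (rise or fall) at any time". None of these places connects the continuous measures to the biomarkers.

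**The concern.** The 50% cut puts a man with a 49% fall in the same class as a man whose PSA doubled, and a 51% fall in the same class as a 99% fall. In the primary test the cut has a purpose, because Section 8.3 takes the 20% null from published rates of 50% decline. The biomarker regression compares men within the trial and uses no such benchmark, so that reason does not carry over.

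At stake is the chance of seeing a moderately informative marker in about 45 men. Section 1.1 presents the biomarker programme as the way to find out who is likely to benefit, and subjects must be willing to have a research biopsy for it.

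**Working it through.** **Inputs from the documents (Section 8.3).** "A sample size of 45 evaluable subjects for PSA response"; response rates from "null hypothesis that the PSA response rate is 20% will be tested against the alternative hypothesis that the PSA response rate is 40"%; "each endpoint will be tested at the one-sided 0.025 (0.05/2) significance level".

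**The plan's own figure.** It is stated as "with 87% power at the one-sided exact test with a significance level of 0.025". The exact rule is at least 15 responses in 45: P(X ≥ 15 | 0.20) = 0.02499 and P(X ≥ 15 | 0.40) = 85.7%. The normal approximation gives Φ[(√45 × 0.20 − 1.96 × √(0.2 × 0.8)) / √(0.4 × 0.6)] = Φ[(1.342 − 0.784) / 0.490] = Φ(1.138) = 87.3%. The stated 87% is the approximate value and is within 2 points of the exact one. So n = 45 and 20-40% are sound inputs. They imply 45 × 0.20 = 9 to 45 × 0.40 = 18 responders in the logistic model.

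**Assumptions, not in the documents.** A standard normal marker with correlation rho to log PSA change; response is the best 20% or 40% of changes; two-sided 0.05.

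**Step 1: idealised normal log ratio.** One value per man, 10,000 simulated trials per cell, n = 45. Power in %:

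| rho | response | logistic (likelihood ratio) | linear on log ratio | Spearman | gain, linear | gain, Spearman |
|---|---|---|---|---|---|---|
| 0.3 | 20% | 30.3 | 53.8 | 49.0 | 23.5 | 18.7 |
| 0.3 | 40% | 36.9 | 52.6 | 47.5 | 15.7 | 10.6 |
| 0.4 | 20% | 49.2 | 79.3 | 74.1 | 30.1 | 24.9 |
| 0.4 | 40% | 59.6 | 78.3 | 73.6 | 18.7 | 14.0 |
| 0.5 | 20% | 69.5 | 95.1 | 92.4 | 25.6 | 23.0 |
| 0.5 | 40% | 80.8 | 94.9 | 92.0 | 14.1 | 11.3 |

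In a separate run at rho = 0 (3,000 trials per cell), false-positive rates were 4.9-6.1% (logistic), 4.6-5.4% (linear) and 4.8-5.6% (Spearman), so the gain does not come from a looser test.

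**Step 2: the variable to which the cut is actually applied.** Response by week 9 depends on the lowest PSA in that window. Appendix B draws post-dose PSA at Cycle 1 Day 8 and on Day 1 of Cycles 2, 3 and 4, about weeks 1, 3, 6 and 9. For a man whose PSA rises throughout, the lowest value is usually the first, so his ratio sits near 1 even if PSA has doubled by week 9. With linear log-PSA paths (slope SD 0.8-1.0, visit noise 0.1-0.2, both assumed), one set of runs gave gains of about 8-23 points (linear) and 6-23 (Spearman) over rho 0.3-0.5. Another gave 10-20 and 8-20. About 8-20 is a fair summary. The lower end depends on the assumed noise, and noise in the baseline value as well would reduce the rank gain further.

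**Step 3: sensitivity.**
- rho = 0.2: gain about 4-10 points, depending on the variable and method.
- rho = 0.6, idealised ratio, linear: 5-14 points, because both analyses already have high power.
- Heavy-tailed changes (t with 3 degrees of freedom), rho 0.3-0.5: linear −5 to +17; Spearman +2 to +28.
- Raw percent change instead of the log ratio, normal case (log-ratio SD 0.8 assumed): only 5-19 points, because percent change is skewed.

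**The case against.** The strongest reply is that 8.5 answers the question it sets. It asks for predictive accuracy for the PSA response and rPFS endpoints, which are the two primary endpoints, and logistic and Cox models match them. That stands, and it is why the logistic model should stay. A reader might infer that it ought to be demoted to a supportive role; that would replace the stated target with another, and nothing in the documents calls for it.

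A reader might also infer that Appendix E asks for the percent change in place of a cut. It does not. It says what to record and to show it in a waterfall plot, and is silent on biomarker models.

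A third tempting inference is that the whole programme rests on 9-18 responders and that adjustment for LDH or haemoglobin is therefore impossible. The same sentence of 8.5 puts the same factors into the Cox model. At 6-month rPFS rates of 20-40%, that model would have roughly 45 × 0.60 = 27 to 45 × 0.80 = 36 events by 6 months, ignoring censoring. Section 8.5 also fixes no number of covariates, so a claim of too few responders cannot be settled from the text.

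Finally, 8.5 describes these analyses as mostly descriptive, attaches no alpha, power or decision rule to them, and would not prevent a later analysis of PSA change. This limits the importance of the point but does not remove it: naming the scale in advance avoids choosing it after the results are seen.

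**Conclusion.** The point holds as a minor one. As written, 8.5 uses only the yes/no cut for the PSA side of the biomarker question, although the size of the change is available. With rho 0.3-0.5, roughly normal changes, two-sided 0.05, n = 45 and 20-40% response, the cut costs about 8-20 points of power against the lowest PSA to week 9 over baseline.

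A reader of the idealised table might infer a general loss of up to 30 points. The documents do not support that: they give neither a marker effect nor a PSA-change distribution, and the lowest-PSA variable is not a normal log ratio. At rho 0.2 the cost is about 4-10 points, and with heavy-tailed changes a linear model may gain nothing or lose a little, while ranks still gain. The primary tests, the secondary endpoints and the Cox model are unaffected.

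**What to change.** In 8.5, pre-specify beside the logistic model a rank-based regression, or a linear regression on the log ratio, of PSA change up to week 9. Use the same baseline factors and combinations and report a concordance index. Ranks are the safer choice if heavy tails are likely; raw percent change should not be used in a linear model.

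Two outcome variables are available, and the SAP should name one:
- Lowest PSA to week 9 over baseline. It exists for every man with a post-dose PSA in that window, but does not separate a stable PSA from one that rises throughout.
- The Week 9 change already derived in 8.4.3. It does separate them, but will be missing for men without a PSA at that visit.

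Keep the logistic model, because it matches the stated PSA response endpoint, and leave the Cox model and the primary tests as they are. The cost is a sentence or two in 8.5 and one more model per marker, with an effect expressed as a PSA ratio or rank rather than an odds ratio. No new data are needed.

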Hence, a sample size of 45 evaluable subjects will provide between 68-99% power to detect a true PSA response rate or 6-month rPFS rate between 35-50% at the one-sided 0.025 significance level.

A sample size of 45 subjects will also be adequate for estimating toxicity rates with sufficient accuracy. Specifically, toxicity rates will be estimated with a standard error of less than 8% and the corresponding 95% confidence intervals will be no wider than 30%.

In order to account for unevaluable (for assessing PSA response or 6-month rPFS rate) subjects, 55 subjects in total will be enrolled.

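### Section 8.5 measures biomarker accuracy by a c-index with no internal validation or optimism correction, so read as written it is an in-sample value that is biased upward

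*Combined protocol and SAP*

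**What the plan says.** The exploratory objective in Section 2.3 is "To associate predictive biomarkers with clinical outcomes to Sacituzumab Govitecan". Section 8.5 makes the predictive accuracy of potential biomarkers, for PSA response and for rPFS, an exploratory endpoint. The tools are "A Cox proportional hazards regression model (for the rPFS endpoint) and a logistic regression model (for the PSA response endpoint", applied to baseline factors "both alone and in combination with other biomarkers (e.g., clinical parameters, LDH, Hb". For each model, "the c-index will be used to quantify the predictive accuracy of these biomarkers".

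Nothing more is said about how the c-index is obtained. Section 8.5 mentions no resampling, cross-validation, penalisation, limit on the number of predictors, interval for the c-index or validation set, and no other section supplies one. It also says of the exploratory work: "These analyses will be mostly descriptive for future references".

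The data available are set in Section 8.3: "A sample size of 45 evaluable subjects for PSA response" is the target, and "55 subjects in total will be enrolled".

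**The concern.** A model fitted to a small data set adapts to the chance features of that data set. If it is then scored on the same subjects, the c-index rewards that adaptation, and even predictors unrelated to outcome score above 0.50. The effect grows with the number of predictors and shrinks with the number of responders or events. Here responders may number only 9 to 18.

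Section 1.1 gives identifying patients likely to benefit as a purpose of the correlative program, and Section 5.5 lists finding markers of response or resistance as its first aim. The c-index is the only accuracy measure planned. If it is uncorrected, a later study could take a value near 0.7 as support for a marker panel when noise alone would often give as much in a model of several factors.

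**Working it through.** **The plan's own figure.** The documents give no c-index value or target. The nearest figure that can be checked is the power statement that fixes the sample size. In Section 8.3 "the null hypothesis that the PSA response rate is 20% will be tested against the alternative hypothesis that the PSA response rate is 40"%, with N = 45 and one-sided 0.025. The exact binomial rule is at least 15 responders of 45, with exact type I error 0.02499 and exact power 85.7%. The normal approximation gives Φ[(0.20·√45 − 1.96·√0.16)/√0.24] = 87.2%. The stated 87% is reproduced to within two points, so the sample size and response rates below are those of the plan.

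**Inputs from the documents**
- Subjects: N = 45 evaluable (55 enrolled).
- Responders: 0.20 × 45 = 9 to 0.40 × 45 = 18.
- Models: logistic for PSA response and Cox for rPFS, with factors alone and combined.

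**Assumptions, because the documents are silent**
- Number of predictors k: 1 for single-factor models, 3 to 8 for combined models. One marker added to LDH and Hb already makes 3.
- Censoring for rPFS: about 20%, with 0% and 40% as a range.
- Predictors: independent standard normal noise, so the true c is 0.50.

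**Method.** Simulate outcome and noise, fit the model, and score it on the same data. For the logistic model, c = [R − n₁(n₁+1)/2]/(n₁n₀), where R is the sum of the ranks of the responders' fitted scores, and n₁ and n₀ are the numbers of responders and non-responders. For the Cox model, c is the share of usable pairs in which the subject with the earlier event has the higher fitted score. There were 1,000 data sets per logistic setting and 600 per Cox setting.

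**Mean in-sample c-index for pure noise, N = 45**

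| Predictors | Logistic, 40% responders | Logistic, 20% responders | Cox, 20% censored | Cox, 0% to 40% censored |
|---|---|---|---|---|
| 1 | 0.570 | 0.589 | 0.542 | 0.536 to 0.545 |
| 3 | 0.640 | 0.677 | 0.581 | 0.572 to 0.590 |
| 5 | 0.689 | 0.733 | 0.610 | 0.599 to 0.630 |
| 8 | 0.746 | 0.805 | 0.641 | 0.632 to 0.669 |

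A repeat of the simulation gave values within about 0.02 of these: 0.79 for the largest logistic entry, 0.65 for Cox with 8 predictors and 0.58 for the largest single-factor entry. With N = 55, 5 predictors and 40% responders, the logistic mean is 0.669, so full enrolment changes little.

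These are averages, and one trial can land higher. With 5 noise predictors at N = 45, the 95th percentile of the logistic c-index is 0.801 at 40% responders and 0.870 at 20%.

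**Effect of a bootstrap correction.** Corrected c = apparent c − mean over resamples of [c of the resample-fitted model in its own resample − c of that same model in the original data]. This was run for the logistic model only, with up to 100 noise data sets per setting and 60 resamples each.

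| Responders | Predictors | Apparent | Corrected | Share of excess over 0.50 removed |
|---|---|---|---|---|
| 40% | 3 | 0.634 | 0.535 | 0.099/0.134 = 74% |
| 40% | 5 | 0.674 | 0.538 | 0.136/0.174 = 78% |
| 20% | 3 | 0.665 | 0.547 | 0.118/0.165 = 72% |
| 20% | 5 | 0.730 | 0.577 | 0.153/0.230 = 67% |
| 20% | 10 | 0.840 | 0.638 | 0.202/0.340 = 59% |

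The correction removes most of the bias. With 5 predictors and about 9 responders, noise still averages about 0.58.

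**The case against.** The strongest reply is that Section 8.5 does not say which data the c-index is computed on. An analyst could follow the text and still apply a bootstrap, so calling the value in-sample is an inference from silence. That is correct as to the wording. Yet the trial has a single treatment cohort of at most 55 subjects, no second data set is described, and the c-index is attached to each fitted model with no further step. An analyst who does only what is written will report the in-sample value.

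A second reply is that the analysis is exploratory and mostly descriptive, that the same models are also used to assess prognostic significance, and that no threshold, go/no-go rule or treatment decision uses the c-index. This stands and limits the severity. It does not remove the bias, because a descriptive figure should still estimate the quantity it is named for.

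A third reply concerns the reach of the numbers. A reader might infer that 0.64 to 0.80 is what this sample size produces in any model. The documents do not support that: they give no number of predictors, single-factor models are also planned and show much less bias, and most of the Cox range lies below 0.64. A reader might also infer that a false marker will be carried forward. Nothing in the documents makes that follow.

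**Conclusion.** The point holds in limited form. The accuracy measure is specified without internal validation, and read as written it overstates accuracy. The size is conditional. With an assumed 3 to 8 noise predictors and N = 45, the average excess over 0.50 is about 0.14 to 0.30 for the logistic model at 20-40% responders, and about 0.08 to 0.15 for the Cox model at about 20% censoring. For single-factor models it is about 0.04 to 0.09.

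The figures assume independent noise predictors that are fixed in advance. They do not include the further inflation from choosing the best of many markers. The primary and secondary analyses are untouched. The change is desirable, not essential.

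**What to change.** Add to Section 8.5, for both the logistic and the Cox models:

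- Report the bootstrap optimism-corrected c-index with a 95% interval beside the apparent value. Use, for example, 500 resamples, and repeat any variable selection within each resample.
- State for each model the number of candidate predictors considered and the number of responders (logistic) or rPFS events (Cox). The reader can then judge how much optimism may remain after correction.

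The cost is a sentence or two in the plan, a few lines of code and a little more analysis time. No further subjects, samples or visits are needed. The drawback is that the reported c-index will be lower.
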